2.5.3 Contact Information

Correct contact information is of high importance for the long term success of this study. Any incorrect information entered affects the study's follow up time point visits.

2.5.3.1 PHONE NUMBER/ADDRESS

Under no circumstances enter bogus information

Example: [contact] or [contact]

Completely write out the city full name and zip code. No abbreviations should be used.

Clearly indicate if residence is an apartment or a house.

Verify with subject that the information was correctly entered in RedCaps

Example: Incorrect: [name]

Correct: [name]

2.5.3.2 EMAIL

Email address is an essential component to this study. It is used to create a MyAgile Account and as a method of follow up. If subject does not have an establish email address one will need to be created for them (see Appendix 3.5). If an email was created for Subject and or Supporter clearly indicate a comment in RedCaps.

DO NOT enter fabricated Emails

Example: [contact]

[contact]

[contact]

2.5.4 Surveys

Enrollment, 6 Months, and 12 Months surveys need to be completed in order. There is no reason why surveys should completed out of order.

DO NOT rush supporter when completing survey. Questions can be sensitive to supporter and such they do have the right to not answer specific survey questions. If supporter declines to answer specific questions a note must be entered in the comment section of that specific question.

RA needs to thoroughly ask all questions as seen in the survey regardless of previous answers. In other words, DO NOT make assumptions bases on previous responses. Be courteous, respectfully and professional with supporter

2.5.5 Compensation

All gift cards are tracked and accounted for. Note that during enrollment NO compensation is provided to Supporter.

2.6 RANDOMIZATION

Envelopes are located in the Research Lab Room drawer. All envelopes are accounted for and under no circumstances should be tampered with. This process is **ONLY** to be completed at the time Supporter verbally consents and agrees to participate in study. All envelopes are in order and thus need be used sequentially.

Once Supporter verbally consents to participate, grab a sealed unused envelope. Randomization will occur after Supporter completes enrollment survey and study requirements. Randomization Form in RedCaps will need to be completed delineating which arm was the Supporter assigned to.

Open envelopes will be placed with the enrollment package, to allow staff to determine participant's supporter was enrolled. Under no circumstances throw away envelop and its context.

[figure not shown]
3.0 APPENDIX

3.1 ORCHID/FIRST NET

[figure not shown]
- Double-click on ORCHID icon

[figure not shown]
- Double-click on FirstNet icon

- Enter your log in information

- Click No when a message appears stating “You are currently listed as an unavailable provider do you want to checked in as an available provider”

[figure not shown]

- Click on the filter tab as seen bellow and scan through the following areas
 - North USC
 - East USC
 - West USC
 - Resus USC
 - Obs USC
 - Supertrack

Note: West Patients should be screened/approached first due to rapid turn over

[figure not shown]

3.3 HOW TO USE THE HbA1c ANALYZER

Proper handling of the HbA1c analyzer is necessary for the accurate assessment of patient HbA1c levels. The following sections outline how to properly run controls and measure a patient's HbA1c levels using the AfinionS100 HbA1c Analyzer.

Remember to always turn the analyzer ON at the beginning of your shift if you are the first shift of the day, and to turn it OFF if you are the last shift of the evening before leaving the FOD.

3.3.1 FINGERSTICK INSTRUCTIONS

Before collecting a blood sample for the HbA1c test, patient's need to be informed what the test consists of. Patient's will receive their HbA1c levels within 10-15 minutes after sample collection. Advice and medical recommendations of Patient's HbA1c level or DM care is not permissible. Report HbA1c value to patient once. For Patient specific questions regarding HbA1c results and or DM Care, please direct them to their primary care provider, care provider in the ED, and or nurse. A1C Level Information sheet can be provided to them. Refer to section 8.2. A1c Information Sheet -English & Spanish in Manuel of Operations.

- Gather ALL of the following supplies after patient agrees to have their HbA1c measured:
 - Kidney Bin
 - Gauze sponge 2x2
 - Alcohol preps
 - Finger bandage
 - Gloves
 - Extra-Absorbent pad
- Hands must be washed/sanitize before encountering any patient
- Gloves must be worn at all times while collecting an HbA1c sample
- All the supplies needed for collecting blood specimen must be placed on top of the extra-absorbent pad to prevent any contamination
- Identify selected site for finger stick (See Figure 3.3A)

[figure not shown]

Figure 3.3A

- Wipe patient's finger with alcohol prep in CIRCULAR motion moving germs away from selected site (See Figure 3.2 B)
- DO NOT wipe side to side

[figure not shown]
[figure not shown]

Figure 3.3B

[figure not shown]
- Let alcohol dry off before proceeding to the finger stick
- For a finger stick, the cut should be PERPENDICULAR to the fingerprint line (See Figure 3.2 B). This will provide the best possible drip and blood flow. Be sure to squeeze finger if blood flow is minimal.
- Wipe off the initial sample of blood with the gauze, and collect the following sample.

3.3.2 COLLECTING CAPILLARY SPECIMEN

To collect sample, remove the capillary from the Test Cartridge, fill the capillary (holding the patient's finger almost horizontal bringing the tip of the capillary in contact with the sample), and immediately place capillary back into the test cartridge. Do not wipe off the capillary after collecting the sample. (See Figure 3.3C)

Do not lay the cartridge on its side, and be sure to hold the cartridge from its handle. Do not touch the optical reading area. This can influence the reading measured. (See Figure 3.3D)

Properly dispose of the finger stick needle, alcohol swab, and gauze in the biohazard container.
(Anything that comes into contact with patient's blood)

The time from filling the capillary until analyzing the Test Cartridge should be as short as possible. Politely excuse yourself to analyze the sample as quickly as possible.

Touch  on the HbA1c analyzer and insert the cartridge with the barcode facing left.

Close the lid manually. The analyzer will start processing the sample automatically.

Record the result, then touch  to accept.

[figure not shown]
Remove the test cartridge from the cartridge chamber and discard it in the biohazard container in the FOD.

Keep the lid of the analyzer closed after in order to protect the analyzer from any damage.

3.4 CREATING PT/SUPPORTER PROFILE

Visit <https://redcap.sc-ctsi.org/> and login with your account information to create a RedCap Patient/Supporter Profile.

1. Click on the 'My Projects' tab and locate TEXTMEDFANS2017. You are now ready to create a new patient profile.
2. Click on Add/Edit Records under the Data Collections section. Select the correct arm for the patient/supporter. (English Patient/Supporter or Spanish Patient/Supporter)
 - Enter the correct study ID in the empty box highlighted below.
 - The next sequential ID can be found in the Manual of Operations in the section 7.1. PID Log Copies.
 - Once you enter the ID and click outside of the highlighted box the profile will be automatically created.
 - BE CAREFUL when creating the ID make sure to be accurate.
 - All patient ID's are assigned the letter P after them. For example, patient ID 50 would be recorded as 50P.
 - All supporter ID's are assigned the letter S after them. For example, supporter ID 50 would be recorded as 50S.

3. First, record the e-mail for a patient/supporter. If the patient/supporter does not have an e-mail, then you must create one for them using the iPad. At the end of each section, change the form status to 'Complete' and click on 'Save and go to Next Form'.

The screenshot shows the REDCap form for 'Email' under the 'Enrollment (Arm 1: Patient English)' event. The 'Study ID' field is highlighted with a red box. A thought bubble points to the 'Study ID' field with the text 'Refer to MOP Section 7.1 for the next sequential PID Number'. The 'Form Status' is set to 'Complete'.

4. Next, complete the physiologic measurements. (weight, height, abdominal circumference, and BP)
5. In the Demographics section, 'Healthy Start Date' for all patients is the 3rd Monday after Patient Enrollment
 - Be sure to record all phone numbers and addresses accurately. This is imperative for future appointment contacts with our enrolled patients.

The image shows a screenshot of a patient enrollment form. The form is divided into several sections. The top section is yellow and contains the text "Event Name: Enrollment (Arm 1: Patient English)". Below this is a grey section for "Study ID". The next section is green and contains the "RA Name" field, which is highlighted with a red box and has a red callout bubble above it that says "RA's complete name DO NOT initial". Below the RA Name field is a grey section for "Date subject signed consent", which has a red callout bubble above it that says "3rd Monday from Patient Enrollment". The final section is grey and contains the "Healthy Start Date:" field, which also has a red callout bubble above it that says "3rd Monday from Patient Enrollment". The form includes various input fields, dropdown menus, and a "Today" button for date selection.

RA's complete name
DO NOT initial

Event Name: Enrollment (Arm 1: Patient English)

Study ID

RA Name
* must provide value

Date subject signed consent
* must provide value

[figure not shown]
Healthy Start Date:
* must provide value

3rd Monday from
Patient Enrollment

3.5 CREATING AN EMAIL

Use the following steps to create an account for participant or supporter

1. Open the following link <https://www.google.com/gmail/about/#>
2. Click on “Create an Account”

3. Complete required fields seen below and Click on “Next Step”

Create your Google Account

One account is all you need
One free account gets you into everything Google.

Take it all with you
Switch between devices, and pick up wherever you left off.

Name

First Last

Choose your username

@gmail.com

Create a password

Confirm your password

Birthday

Month Day Year

Gender

I am...

Mobile phone

Your current email address

Default homepage

Set Google as my default homepage.

Your default homepage in your browser is the first page that appears when you open your browser.

Location

United States

[Next step](#)

[Learn more](#) about why we ask for this information.

4. Privacy and Terms Window will appear. Click on “I Agree”

Privacy and Terms

By choosing "I agree" below you agree to Google's [Terms of Service](#).

You also agree to our [Privacy Policy](#), which describes how we process your information, including these key points:

Data we process when you use Google

- When you set up a Google Account, we store information you give us like your name, email address, and telephone number.
- When you use Google services to do things like write a message in Gmail or comment on a YouTube video, we store the information you create.
- When you search for a restaurant on Google Maps or watch a video on YouTube, for example, we process information about that activity – including information like the video you watched, device IDs, IP addresses, cookie data, and location.
- We also process the kinds of information described above when you use apps or sites that use Google services like ads, Analytics, and the YouTube video player.

Depending on your account settings, some of this data may be associated with your Google Account and we treat this data as personal information. You can control how we collect and use this data at [My Account](#) ([myaccount.google.com](#)).

Why we process it

We process this data for the purposes described in [our policy](#), including to:

- Help our services deliver more useful, customized content such as more relevant search results.

CANCEL

I AGREE

5. Help participant record their username name and password for their records
6. Do NOT keep a copy of participant's log-in information
7. Provide participant with a copy of email safety tips form

**Introduction:**

This statistical analysis plan contains This data analysis plan (DAP) contains definitions of study period, study groups/cohorts, data elements and statistical methods for understanding the effects of an intervention to improve diabetes specific behaviors and glycemic control among Emergency Department patients with poorly controlled diabetes.

**Background:**

Although diabetes is a nationwide epidemic, US Latinos are a particularly vulnerable population. Latinos are more likely than non-Latino Whites to develop diabetes and have higher rates of diabetic complications and diabetes related mortality. This disparity is prominent in Los Angeles County, where almost half the residents are Latino, and diabetes prevalence is higher than the national average. Patient with diabetes who rely on the Los Angeles County + University of Southern California Emergency Department for care are a high need population, with poor glycemic control, low diabetes knowledge, and limited access to care. These patients are not often adequately served by the current healthcare system, and require dedicated attention to address their unique health needs and barriers to care.

Culturally and linguistically appropriate interventions can combat this disparity, especially social support interventions. Training family members and peers to support patients with diabetes has been shown to improve patient motivation, healthy behaviors and glycemic control, and is accepted by Latino populations. However, traditional social support interventions require in-person training for family and friends, as well as physical space and personnel for training.

Additionally, support training is often provided to the most proximate people to the patient with available time, rather than the most influential person identified by the patient. In-person training also limits scalability in populations with limited transportation and financial resources. Strategies to decrease these barriers are needed; mobile health (mHealth) may be a solution.

mHealth is the use of mobile phones to provide public health and medical solutions. mHealth interventions improve disease management of chronic illnesses, including diabetes.

However, existing app-based mHealth interventions require smartphones, which are not widely used in resource-poor communities such as safety-net emergency departments (EDs).

However, Latino populations have high rates of mobile phone ownership, text-message use, and access health information via mobile phones more frequently than other digital sources.

Latino patients from low-resource settings have enthusiastically joined text-message and interactive voice-recording interventions to improve diabetes self-care.

ED care is an opportunity to reach patients and families during a health crisis, when they are susceptible to behavior change. As emergency care is more expensive than healthcare in other sites, ED interventions should maximize the benefit of these visits through improved behaviors and health outcomes. ED-based interventions can also bridge patients until primary care can be established for those lacking primary care, or during the wait for the next visit for patients with limited access to a primary care provider.

In this statistical analysis plan, we describe the design and analysis procedures for the randomized controlled trial TEXT-MED+FANS (Trial to Examine Text-Messaging in Emergency patients with Diabetes+ Family and friends Network Support), adding a mobile social support module, FANS to the TEXT-MED intervention to provide emotional context and highly personal touch. TEXT-MED+FANS uses mHealth to overcome the transportation and time obstacles that social support solutions face by offering social support training via a mobile platform. Using mobile training, a patient can select the most influential person to support them, rather than the most proximate.

### **Study Objectives:**

#### Primary Objective:

1. Examine the change in percent glycosylated hemoglobin at 6 months for FANS supported patients vs non-augmented support patients.

#### Secondary Objectives:

1. Examine the change in percent glycosylated hemoglobin at 12 months for FANS supported patients vs non-augmented support patients.
2. Examine changes in psychosocial and behavioral outcomes at 6 and 12 months for FANS supported patients vs non-augmented support patients.

### **Study Design:**

In this twelve-month, comparative effectiveness randomized controlled trial (enrollment period July 2017 to October 2018), ED patients with poorly-controlled diabetes mellitus from an urban,

safety net medical center were randomized to one of two arms: [1] an mHealth intervention for self-management education augmented by mHealth augmented social support (TEXT-MED+FANS) or [2] the same patient-oriented mHealth intervention with minimally augmented social support (TEXT-MED + pamphlet).

**Patient recruitment**

Patients were recruited from July 2017 to October 2018. IRB approval for this study was obtained prior to study initiation from the USC Health Sciences Institutional Review Board. This study enrolled ED patients with both type I and type II diabetes at LAC+USC (Los Angeles County + University of Southern California Medical Center). ED patients with diabetes in this healthcare system have been found to have poor glycemic control, poor diabetes specific knowledge, and poor access to primary care.

Screening, Eligibility Criteria and Recruitment

Table 1: Eligibility criteria for participants

Exclusion Criteria
Psychiatric involuntary hold, or in police custody
Altered mental status
Clinically unstable to consent and complete baseline assessment
Inclusion Criteria
Age 18 or greater

Stable ownership of mobile phone
Able to send and receive text messages
Reads English or Spanish
A1C 8.5 or greater
Identifies a support person who can be contacted within 2 weeks to enroll

Trained research assistants (RA) conducted screening and enrollment during the daytime and evening hours in the LAC+USC ED. They surveyed the ED electronic patient tracking system for patients with diabetes. Inclusion and exclusion criteria are listed in Table 1. Only subjects with A1C  $\geq 8.5\%$  were enrolled in this trial, as these patients have the greatest need for intervention and potential to demonstrate beneficial intervention effect. The A1C-based eligibility requirement was verified in the emergency department during the patient's visit, using the Afinion AS-100 capillary point-of-care A1C meter (Axis-Shield PoC AS, Oslo, Norway). Patients who reported both type 1 and 2 diabetes were enrolled, as prior work with this population has shown that 30% of patients are unsure which type of diabetes they have. RAs explained the purpose of the study and obtained written informed consent in the language of the patient's preference. To be eligible, patients had to identify a family member or friend to agree to serve as a supporter. Patients were aware at enrollment that the designated supporter could receive multiple text-messages per day, and would be prompted to offer increased support.

#### Enrollment & Randomization

The goal of this investigation is to study augmenting existing social support via mHealth, so patients were only eligible to be enrolled in the study if a supporter agreed to participate as well; however, this took up to three weeks to contact and enroll the supporter. Given the potential lag, all potentially eligible patients were registered in the SHERPA platform used by Agile Health while in the ED. Occasionally, patients lacked cellular service in the ED and were not able to text-in the Federal Communications Commission-required YES message to opt in during their initial ED visit; we texted and called these patients daily for up to one week until they texted back in YES. The supporter was not contacted until after the patient was fully registered in the system. If a supporter was not eventually enrolled as well, the patient still received the patient text-messaging program, however they were removed from further participation in the study.

Supporters were enrolled either in the ED during the initial contact with the patient or remotely by telephone if they were not present in the ED. Each patient was instructed to rank up to three family or friends who would provide them the most support. As the intervention encourages communication between a patient and a supporter, only one supporter was enrolled per patient to not overwhelm patients with suggestions for healthy living from multiple loved ones. We collected multiple contact numbers for each potential supporter from each patient. We called daily for up to three weeks to enroll supporters.

Enrolling supporters consisted of verbal consent, confirming age>18 and the ability to send and receive text messages, completion of supporter survey instruments and registration in the

SHERPA platform. Registration in the SHERPA system required a YES text back from the supporter. If the supporter did not respond with the required text-in YES message, we called them daily to remind and assist them with completing registration. After supporter enrollment was completed, the dyads were randomized to the FANS mHealth-augmented social support or pamphlet-based social support education for the supporter. All patients received the TExT-MED patient program.

### **Classification of Study Groups:**

1] **Intervention Group:** Patients who received an mHealth intervention for self-management education augmented by mHealth augmented social support (TExT-MED+FANS) sent to an identified loved one

[2] **Active control group:** Patients who received the same patient-oriented mHealth intervention with minimally augmented social support (TExT-MED + pamphlet)

### **Study Measures, Definitions and Rationale for Selection:**

#### Clinical Outcomes and Biologic Measures:

Glycemic control is measured by hemoglobin A1C collected at point-of-care from an Afinion AS100 capillary point of care machine. The Afinion machine has excellent point of care correlation with laboratory values. As a surrogate for average glycemic control over the previous 3 months and with correlation with clinical outcomes, hemoglobin A1c is a marker of overall clinical disease management.

Systolic blood pressure mmHg: Blood pressure is measured by study RAs after the patient is seated for 5 minutes, with the average of three readings used as the systolic blood pressure for that visit. Systolic blood pressure is associated with cardiovascular complications

BMI: calculated from Weight and Height. As a measure of adiposity, it correlates positively with cardiovascular disease outcomes. While imperfect, it is an easily measured and validated marker.

Weight in lbs. Participants are weighed on the same scale at enrollment and follow up assessments, without shoes or overclothes. If patient is unable to stand at time of enrollment due to pain or illness, weight as recording by nursing staff in the medical records will be used.

Height: measured by RAs at enrollment without shoes while participant is standing.

Abdominal circumference (cm): A measure of central adiposity, it correlates with cardiovascular outcomes.

#### Healthy behavior measures:

Summary of Diabetes Self-care Activities . The Summary consists of 6 subscales representing different domains of diabetes related healthy behaviors and self-care. It has been validated in over 10 studies, with the results published in two manuscripts: one with three studies , and

one with seven studies. Each measure ranges from Each range from 0-7, indicating number of days per week patient reports engaging in these behaviors.

1. Following a generally healthy diet
2. Following a disease specific diet plan
3. Spacing carbohydrates throughout the day
4. Getting sufficient physical activity
5. Checking feet daily for wounds
6. Self-monitoring blood glucose as advised by a healthcare provider

Medication adherence (Wilson 3 item Medication Adherence scale) . The three-item medication adherence scale is a self-report measure that assesses the number of days of medication missed in the last month, the frequency of medication taking, and asks patients self-rate their medication adherence. Initially developed in HIV research, it has been validated for non-HIV medications with electronic drug monitoring and other adherence measures . An individual's total score ranges from 0-100. It is the combination of three sub-scores (days missed dose (negative scored), self-rating, days taking medications as indicated).

Healthcare utilization by the patients' report of clinic appointments, ED visits and hospitalizations with in the 6 months prior to enrollment at each follow up visit. This self-report will be confirmed by a manual review of the electronic medical record.

Psycho-social measures:

Self-efficacy (Diabetes Empowerment Scale Short Form) , is a measure of a patient's overall diabetes related self-efficacy, shortened by the original from 37 to an 8 item scale. It has reliability of  $\alpha=0.84$ ; and has been shown to be sensitive to change in multiple populations and is correlated with improved glycemic control measured by A1C . It ranges from 8-40 points; higher score indicates higher self-efficacy.

Diabetes related distress (Diabetes Distress Scale) , is a 17 item scale measuring distress related to emotional burden, physician-related distress, regimen-related distress, and diabetes-related interpersonal issues. It has a Cronbach's alpha of 0.88-0.93 in various studies. Higher scores are negatively correlated with several healthy behaviors. Each question is a Likert scale ranking of how serious a particular issue is from 1-6, 6 indicating a more significant problem. The scores are then averaged across all item, with final scores ranging from 1-6, with 6 indicating higher levels of distress.

Depression as measured by the PHQ-9 , is a widely used scale of depression used in clinical practice and research. The Cronbach's alpha ranges from 0.86-0.89, and it has been validated in multiple languages. Higher levels of depression are associated with fewer healthy behaviors and worse glycemic control.

Fatalism is measured by the Diabetes Fatalism Scale , which measures three subscale emotional distress, religiosity and coping and perceived self-efficacy. The total score has a

Cronbach's alpha of 0.80 and ranges from 12-72, higher score indicates higher fatalism. The score is associated with glycemic control, depression, self-care behaviors and social factors.

Quality of life (World Health Organization WHO-5 Well Being Index) is a widely used measure of quality life, validated in many languages and consists of only 5 items.

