## **Hypothesis Analysis**

Initial changes in outcomes (primary and secondary) will be compared between groups with paired t-tests. This will be followed by a longitudinal method with a mixed effects regression model to account for correlated outcome data (zero-six month and six-twelve month changes) and loss to follow up. Analyses will be conducted by intent-to-treat, with participants analyzed according to their randomized intervention regardless of adherence.

Because change in A1C is the outcome, participants who drop out prior to six-months will not be included in the analysis. All participants who complete the twelve-month study will provide two outcome measures of six-month change: a zero-six month measure of treatment efficacy, and a six-twelve month measure of sustainability of treatment effect. The linear mixed effects model will include a random intercept term for participants. Fixed effects will include treatment allocation, initial level of A1C (zero month measure for treatment efficacy, six-month measure for sustainability), and a covariate of study period (zero-six month, six-twelve month). The main effect of treatment will test for group differences over both zero-six and six-twelve month periods. An interaction term of treatment by study period will test for differences in treatment effects by study period; treatment effects will be estimated and tested for differences by study period in this interaction model. Model assumptions including normality of model residuals and homogeneity of variance will be evaluated. A sensitivity analysis confined to adherent participants (those who have not opted out of messages and have received 75% or greater of messages confirmed by message delivery platform) will be conducted. Mixed effects linear regression models will be conducted on secondary outcomes as detailed above.

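### Healthcare utilisation rests on patient report at follow-up visits, so patients who leave before month 6 have no value although their in-system visits could be abstracted; the stated window is also wrong as worded

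*SAP*

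**What the plan says.** **Source and window.** Under Healthy behavior measures, the SAP defines healthcare utilisation by the patient's "report of clinic appointments, ED visits and hospitalizations with in the 6 months prior to enrollment at each follow up visit". It then adds: "This self-report will be confirmed by a manual review of the electronic medical record". It gives no rule for disagreement between the two sources, and does not say that the record supplies a count when the patient gives no report.

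**Status.** Utilisation is not named in the objectives or in the statement of primary and secondary outcomes. It enters through its place among the healthy behavior measures, under the secondary objective "Examine changes in psychosocial and behavioral outcomes at 6 and 12 months for FANS supported patients vs non-augmented support patients".

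**Analysis.** Hypothesis Analysis says that "participants who drop out prior to six-months will not be included in the analysis". The reason given is that the outcome is a change in A1C. The section later says: "Mixed effects linear regression models will be conducted on secondary outcomes as detailed above". The mixed model is there "to account for correlated outcome data (zero-six month and six-twelve month changes) and loss to follow up". The same section states: "Analyses will be conducted by intent-to-treat, with participants analyzed according to their randomized intervention regardless of adherence".

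**Follow-up and record access.** Protocol section 2.3.2 makes the 6- and 12-month contacts in-person visits; the 3- and 9-month surveys are remote. All patients came from one ED (SAP, Patient recruitment), were screened through its electronic record (Protocol section 2.3.1 and Appendix 3.2), and have a medical record number entered at enrollment (Protocol section 2.4.2).

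**The concern.** A1C needs a fingerstick at a visit, so a patient who has left cannot supply a six-month change. A count of ED visits, admissions or clinic appointments at the enrolling centre has no such limit. The plan nevertheless makes the count depend on attendance, because the record is consulted only to check a report already given. The A1C exclusion then carries over to an outcome that its stated reason does not fit.

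The result would be a comparison restricted to patients who stayed to month 6, under an intent-to-treat label, for one of the few outcomes that could be obtained on every randomised patient. Attendance may be related both to health-care use and, in an open comparison of two kinds of supporter involvement, to arm.

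A second problem lies in the same sentence. As worded, patients are asked at each follow-up visit about a period that ended before they were randomised.

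**Working it through.** The documents state no sample size, dropout rate, visit rate or standard deviation, so there is no figure to reproduce. The check is mainly a reading of the text, with arithmetic on stated assumptions.

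**1. Who loses what.** Setting the utilisation definition beside the dropout rule and the model for secondary outcomes:

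| Patient | 0-6 month value as planned | 6-12 month value as planned | In-system visits retrievable from the record |
|---|---|---|---|
| Leaves before month 6 | none | none | both periods |
| Attends month 6, lost before month 12 | reported, then checked | none | both periods |
| Attends both visits | reported, then checked | reported, then checked | both periods |

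Complete loss is therefore confined to the first row. The 3- and 9-month remote surveys might fill part of the gap, but the documents do not say whether they ask about utilisation.

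**2. The window.** Taken literally, the month-6 and month-12 questions both concern the six months before enrollment. The two answers would be repeated recalls of one pre-randomisation period, and treatment cannot affect either. The probable intent is the preceding six months, asked at enrollment and at each follow-up, but that is an inference from the model's two periods. The text does not say it.

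**3. Precision.** If a share m of patients is missing equally in both arms, and the variance per patient is unchanged, the standard error of the arm difference grows by 1/sqrt(1 - m). All values of m are assumptions.

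- m = 0.10: 1/sqrt(0.90) = 1.05
- m = 0.20: 1/sqrt(0.80) = 1.12
- m = 0.30: 1/sqrt(0.70) = 1.20
- m = 0.40: 1/sqrt(0.60) = 1.29

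For 20-30% missing, the standard error is about 12-20% larger.

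**4. Bias.** In arm a, let m_a be the share missing, R_a the mean change in visits among those who stay, and N_a the mean change among those who leave. The mean over all randomised patients is (1 - m_a)R_a + m_a N_a, so the error from using stayers only is R_a - [(1 - m_a)R_a + m_a N_a] = m_a(R_a - N_a). The error in the arm comparison is m_1(R_1 - N_1) - m_0(R_0 - N_0). It is zero when the two products are equal, and can take either sign otherwise. The documents give none of these six quantities, so no size can be attached.

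**The case against.** **The record is not complete either.** A reader might infer that every visit by every randomised patient sits in the centre's record. The documents do not support that. They show that each patient can be looked up there. They do not say that the record holds care received elsewhere; a menu entry for community records in an Appendix 3.2 screenshot says nothing about coverage or use for outcomes. This objection stands, and it limits the fix. A patient who leaves and is treated elsewhere would count as zero, and self-report from attenders cannot correct that. If the same share p of visits falls outside the system in both arms, in-system means are (1 - p) times the true means: the ratio between arms is unaffected, and the difference shrinks by the factor (1 - p). If p differs by arm, the comparison is distorted.

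**Attrition need not produce a false effect.** A reader might also infer a sizeable spurious difference because heavy users tend to miss visits. The plan analyses change and adjusts for initial level. A steady heavy user has an expected change of zero, so selective attendance by such patients does not by itself bias the unadjusted comparison of change. Some bias can return after adjustment for a noisy baseline count, but its size depends on assumed inputs.

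**The dropout rule is stretched.** It is worded for A1C and for patients who drop out, not for everyone who misses a visit. That is fair: its application to utilisation is an inference from the cross-reference for secondary outcomes. Without it, the patient still has no planned value, because there is no report to confirm.

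**Recall may not be the worse source.** The documents do not compare the two. The SAP's Study Limitations concede only that healthy behaviors are self-reported and that no social desirability measure was included at baseline.

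**Conclusion.** The point holds in a limited form. As written, utilisation depends on a report at a follow-up visit, and patients who leave before month 6 have no value for an outcome whose in-system part can be retrieved without them. Patients lost after month 6 keep their 0-6 month value. The window is wrong as worded and needs correcting whichever source is used.

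The loss of precision is about 12-20% in the standard error if 20-30% are missing. That rests on an assumed rate, equal loss in both arms and unchanged variance. The size and direction of any bias are unknown. The documents do not support a claim that all visits are recorded, or any particular false difference between arms.

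No primary or priority secondary conclusion depends on this measure. It is an inexpensive improvement to a secondary outcome and should be weighed as such.

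**What to change.** Amend the utilisation entry under Healthy behavior measures in the SAP:

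- Take ED visits, hospitalizations and clinic appointments within the health system from the electronic record for every randomised patient, whether or not they attend follow-up.
- Use fixed windows: the six months before enrollment as baseline, then 0-6 and 6-12 months. Name the date from which the windows run, because Protocol section 2.4.8 ties the six-month appointment to the health start date rather than to enrollment. Say how the enrolling ED visit is counted.
- Label the outcome in-system utilisation.
- State which source prevails when record and report disagree.
- As a sensitivity analysis among attenders, add self-reported care received elsewhere to the record counts.

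In Hypothesis Analysis, state that the dropout exclusion does not apply to this outcome and that all randomised patients are analysed by arm.

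The cost is SAP wording and an extension of the planned chart review to patients who did not return; no new visit is needed. If a patient withdraws consent, abstraction would depend on what that patient authorised. The remaining downside is that outside care is missed in the main version, most seriously for non-returners, and the report of results should say so.
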